5.2.3 Secondary Outcomes

Two-way repeated measures ANCOVA with one within-subject factor (time) and one between-subject factor (condition) will be used to compare HbA1c levels, insulin levels, total cholesterol levels, LDL, HDL and triglyceride levels, inflammatory biomarker levels (including IL-6, IL-8, IL-10, CRP and TNF-a), and diastolic and systolic blood pressure. Post-hoc one-tailed paired t-tests will be performed on significant main or interaction effects to compare differences between groups over time. For non-normally distributed outcome variables, robust ANCOVA and post-hoc comparisons with trimmed means are used. In addition, a two-tailed t-test will be used to compare the change in insulin sensitivity from baseline to 16 weeks between treatment and placebo.

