2.0 Study Methods

2.1 Trial design

This trial is a two-arm, individually randomized, single-blind placebo-controlled trial. The total trial duration is 24 weeks. Participants will be assigned to the intervention or placebo for 24 weeks. Primary and secondary outcomes will be assessed at baseline, 16, and 24 weeks (*Section 1.3*).

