2.2 Randomisation

Consenting participants who have met all of the eligibility criteria and completed the baseline assessment will be individually randomised into one of the two groups, using a web based system (Sealed Envelope), at a ratio of 1:1, stratified by gender and BMI.

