2.3 Sample size

This study aims to recruit 60 participants, men and post-menopausal women aged 18-70 diagnosed with pre-diabetes, but not receiving treatment for type 2 diabetes. As this is a pilot study, our sample size has not been derived statistically, but informed based on previous studies assessing fibre-based interventions in pre-diabetes cohorts. Our sample size is therefore consistent with previous studies assessing fibre-based interventions in similar populations. Results from previous studies (Zhou et al. 2018, n = 43; Peterson et al., 2018, n = 68) suggest that 60 participants is an adequate sample size to capture meaningful differences in our primary and secondary outcome measures. A sample size of 30 in each arm results in a power of 80% to detect effects of at least d = 0.74.

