3.0 Statistical Principles

3.1 Confidence intervals and P values

Effects will be considered statistically significant if the associated *p*-value is smaller than 0.05.

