5.1.2 Secondary Outcomes

- HbA1c (%) between baseline, 16 and 24 weeks
- Glucose (mmol/L) between baseline, 16 and 24 weeks
- Insulin (µU/mI) between baseline, 16 and 24 weeks
- Insulin sensitivity (µU/ml) from ISI-OGTT between baseline and 16 weeks
- Total cholesterol (mmol/L) between baseline, 16 and 24 weeks
- LDL (mmol/L) between baseline, 16 and 24 weeks
- HDL (mmol/L) between baseline, 16 and 24 weeks
- Triglycerides (mmol/L) between baseline, 16 and 24 weeks
- IL-6 (ng/L) between baseline, 16 and 24 weeks
- IL-8 (ng/L) between baseline, 16 and 24 weeks
- IL-10 (ng/L) between baseline, 16 and 24 weeks
- CRP (ng/L) between baseline, 16 and 24 weeks
- TNF-a (ng/L) between baseline, 16 and 24 weeks
- Diastolic blood pressure (mm/Hg) between baseline, 16 and 24 weeks
- Systolic blood pressure (mm/Hg) between baseline, 16 and 24 weeks

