5.2.2 Primary Outcome

A two-tailed t-test will be used to compare the percent change in HbA1c levels from baseline to 16 weeks between treatment and placebo.

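### The repeated measures ANCOVA for the secondary outcomes names no covariate, no levels of time and no term that tests treatment; on its natural reading baseline is a response, which usually costs power

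*SAP*

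**What the plan says.** Section 5.2.3 of the SAP gives one model for HbA1c, insulin, four lipid measures, five inflammatory markers and two blood pressures, 13 outcomes in all: "Two-way repeated measures ANCOVA with one within-subject factor (time) and one between-subject factor (condition"). No covariate follows. Neither the baseline value nor the randomisation factors appear, although section 2.2 says that allocation is "stratified by gender and BMI". The section does not list the levels of time.

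The nearest guide to those levels is elsewhere. Section 5.1.2 defines these outcomes in the form "HbA1c (%) between baseline, 16 and 24 weeks", section 2.1 says "Primary and secondary outcomes will be assessed at baseline, 16, and 24 weeks", and the table in section 1.3.2 gives the same three times.

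Follow-up testing depends on the model: "Post-hoc one-tailed paired t-tests will be performed on significant main or interaction effects to compare differences between groups over time". No term is singled out as the test of treatment. The significance threshold (section 3.1) is a p-value that "value is smaller than 0.05".

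**The concern.** An analysis of covariance without a covariate cannot be run as written, so the analyst has to supply the missing part. Taking time to be baseline, 16 and 24 weeks, baseline becomes a third response. Randomisation makes the expected difference between arms zero at that visit. Averaging it into the condition main effect therefore dilutes the treatment effect and adds chance baseline imbalance. The interaction term is not diluted in that way, but it spends two degrees of freedom on a question that is usually about one contrast.

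The choice is also open in a second sense. Main effect and interaction are different tests with different power, and the SAP lets either lead to post-hoc comparisons. Two analysts following section 5.2.3 could reach different conclusions on the same data. At stake is how clearly a 60-person trial can speak about its secondary outcomes. The primary t-test is not affected.

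**Working it through.** **Inputs from the SAP.** 30 per arm and d = 0.74 (section 2.3); alpha 0.05 (section 3.1); two-sided testing, taken from the primary analysis (section 5.2.2: "A two-tailed t-test will be used to compare the percent change in HbA1c levels").

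**Assumptions, because the SAP gives no figures.** Unit variance at each visit, equal correlation r between all visits with r = 0.5, 0.7 or 0.8, and a standardised effect d that is the same at weeks 16 and 24 unless stated.

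**The plan's own figure.** Section 2.3 states: "A sample size of 30 in each arm results in a power of 80% to detect effects of at least d = 0.74". A two-sample t-test with 58 degrees of freedom and noncentrality 0.74 × √15 = 2.87 has 80.5% power, so the figure reproduces. It is the power of a two-group comparison, not of the repeated measures model. The SAP gives none for the latter.

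**Noncentrality of each test, n = 30 per arm.**

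- Condition main effect, three visits. Mean effect (0 + d + d)/3 = 2d/3; variance of a three-visit mean (1 + 2r)/3. So λ = 15 × (2d/3)² ÷ [(1 + 2r)/3] = 20d²/(1 + 2r), tested on F(1, 58).
- Interaction, three visits. Deviations of (0, d, d) from their mean have sum of squares 2d²/3. So λ = 15 × (2d²/3)/(1 − r) = 10d²/(1 − r), on F(2, 116).
- Baseline-adjusted mean of weeks 16 and 24. Residual variance (1 + r)/2 − r² = (1 − r)(1 + 2r)/2. So λ = 30d²/[(1 − r)(1 + 2r)], on F(1, 57).
- Baseline-adjusted single visit. Residual variance 1 − r². So λ = 15d²/(1 − r²), on F(1, 57).

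For d = 0.5 and r = 0.5 the four values of λ are 2.5, 5.0, 7.5 and 5.0.

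**Power, same effect at both visits.**

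| d | r | Condition main effect | Interaction | Adjusted, two-visit mean | Adjusted, one visit |
|---|---|---|---|---|---|
| 0.5 | 0.5 | 34% | 49% | 77% | 59% |
| 0.5 | 0.7 | 30% | 72% | 89% | 76% |
| 0.5 | 0.8 | 28% | 89% | 96% | 89% |
| 0.74 | 0.5 | 63% | 84% | 98% | 90% |
| 0.74 | 0.7 | 56% | 97% | 99.7% | 98% |
| 0.74 | 0.8 | 52% | 99.8% | about 100% | 99.7% |

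Simulation of the d = 0.5 rows gave 35/31/27%, 49/72/89%, 75/88/96% and 58/75/89% for the four columns, within about 2 points of the formulas. At r = 0.9 the interaction (99.6%) and the adjusted mean (99.9%) hardly differ.

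**Effect at one visit only, d = 0.5, r = 0.5.** The interaction keeps λ = 5.0 and 49% power. The adjusted two-visit mean sees d/2, so λ = 7.5/4 = 1.88 and power is 27%. The adjusted test at the affected visit has 59%.

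**The gate to post-hoc tests.** Under these assumptions the condition and interaction tests are close to independent. With no effect, the chance that at least one is significant is 1 − 0.95² = 9.8%. If the time main effect also counts, it is 1 − 0.95³ = 14.3%. With d = 0.5 at both visits, condition or interaction opens the gate in 1 − (1 − 0.343)(1 − 0.493) = 67% of trials at r = 0.5, and in 1 − (1 − 0.276)(1 − 0.888) = 92% at r = 0.8.

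**The case against.** The levels of time are inferred. Section 5.2.3 does not state them, and the word ANCOVA, used again for the robust version, implies some covariate. A model with baseline as covariate and two post-baseline visits is therefore not excluded. This stands, and it is why the point is first one of under-specification. It does not remove the point, because the covariate would still have to be named.

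A reader might infer that every repeated secondary outcome loses power. The documents do not support that. They give no correlation, no effect pattern and no designated treatment term, and the result turns on all three. Against a single-visit adjusted contrast the interaction gives up about 10 points at r = 0.5, about 4 at 0.7 and none at 0.8. If the effect is at one visit only, the interaction beats the adjusted average.

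A reader might also infer that the omnibus step blocks real effects. The wording lets any significant main or interaction effect open it. Condition or interaction does so in 67% to 92% of trials at d = 0.5, and adding the time effect raises this to 83% to 99% in simulation. The clearer weakness is the opposite one: it opens too readily with no effect.

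Finally, this is a proof-of-concept trial whose size was not derived statistically, it claims no power for secondary outcomes, and the time-by-condition interaction is a valid test. All true. Nor does treating baseline as a response cost power in itself: a longitudinal model that constrains the arms to equal baseline means avoids the loss. Section 5.2.3 specifies no such constraint.

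**Conclusion.** The point holds as a defect of specification with a usual, but not universal, cost in power. Section 5.2.3 leaves out the covariate, the levels of time and the treatment term. On the natural reading, a sustained effect is cut to two thirds in the condition main effect, which is the weakest test in every row of the table above. The interaction is clearly weaker than a baseline-adjusted average at low to moderate correlation, and roughly level with a single-visit contrast at high correlation. Accepting either term as the gate roughly doubles the nominal 5% chance of proceeding when there is no effect. These sizes rest on equal variances, equal correlations between visits and complete data on 60 participants, none of which the SAP gives for these outcomes. The change is worth making because it is cheap and removes the ambiguity whichever reading was meant.

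**What to change.** Rewrite the model in section 5.2.3. For each repeated secondary outcome, take the week-16 and week-24 values as responses, with arm, visit, arm-by-visit, baseline value and the randomisation strata (gender and BMI, as used in the allocation) as terms. Report the two-sided between-arm difference with 95% CI at each visit and averaged over both visits. Reporting both covers a sustained effect and one confined to a single visit. Let these estimates replace the omnibus gate and the post-hoc tests that follow it, and state which of them leads. Name the same covariates for the robust version.

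The cost is SAP wording and a few model degrees of freedom. Baseline values and strata are already collected, so no new data are needed.

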1.3.2 Secondary Objectives

Secondary Objective	Outcome Measure	Timepoint(s) of evaluation of this outcome measure
To compare the effect of the Myota Metabolic Regulator versus placebo on:		

HbA1c	Change in HbA1c	Baseline, 16 and 24 weeks
Insulin	Change in Insulin	Baseline, 16 and 24 weeks
Insulin sensitivity	Insulin sensitivity, measured using ISI-OGTT	Baseline and 16 weeks
Lipid profile	Cholesterol [total, LDL, HDL] and triglycerides)	Baseline, 16 and 24 weeks
Inflammatory markers	IL-6, IL-8, IL-10, CRP, TNF-a	Baseline, 16 and 24 weeks
Blood pressure	Diastolic and systolic blood pressure	Baseline, 16 and 24 weeks
To investigate the safety of the Myota Metabolic Regulator	Evaluation of overall safety of the Myota Metabolic Regulator by the monitoring of: • Number of AEs • Number of SAEs	Continuously for the duration of taking the intervention/placebo
To investigate intervention adherence	Intervention adherence questionnaire	Daily for the duration of the intervention, 24 weeks
To investigate usability	Usability questionnaire	At 16 and 24 weeks

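### The post-hoc tests for the secondary outcomes are one-tailed paired t-tests, which cannot compare independent arms, and a time effect shared by both arms is enough to open them

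*SAP*

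**What the plan says.** SAP section 5.2.3 fits a repeated-measures ANCOVA with time as the within-subject factor and condition as the between-subject factor. It covers HbA1c over time, insulin, lipids, inflammatory markers and blood pressure. The follow-up rule is: "Post-hoc one-tailed paired t-tests will be performed on significant main or interaction effects to compare differences between groups over time". For non-normal outcomes, "robust ANCOVA and post-hoc comparisons with trimmed means are used". Section 3.1 applies p < 0.05 to all effects and does not distinguish one-tailed from two-tailed tests.

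The objective behind these analyses, in section 1.3.2, is "To compare the effect of the Myota Metabolic Regulator versus placebo on" the listed outcomes. Section 2.1 describes the design: "This trial is a two-arm, individually randomized, single-blind placebo-controlled trial". Under section 2.2, participants are "individually randomised into one of the two groups".

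Elsewhere the SAP tests between arms and two-tailed. For the primary outcome (section 5.2.2): "A two-tailed t-test will be used to compare the percent change in HbA1c levels from baseline to 16 weeks between treatment and placebo". For insulin sensitivity (section 5.2.3): "a two-tailed t-test will be used to compare the change in insulin sensitivity from baseline to 16 weeks between treatment and placebo".

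**The concern.** The post-hoc sentence has three separate faults.

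1. **Test and purpose do not match.** No participant in one arm is paired with one in the other. A paired t-test, within one arm or on both arms pooled, tests change between visits. The sentence says it compares groups.
2. **The gate is too wide.** A main effect of time that is the same in both arms carries no information about the product, yet it opens the tests. A significant time-by-condition interaction is not required.
3. **One tail, not named.** One-tailed p < 0.05 corresponds to a two-sided level of 0.10. The background (sections 1.2.1 and 1.2.2) suggests the hoped-for direction for glycaemic and inflammatory outcomes in general terms. For HDL it is unclear, because the synopsis lists high HDL beside high LDL as a feature of pre-diabetes.

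At stake is how nearly all the secondary efficacy results are read. A drift common to both arms can open the tests and, by chance, reach significance in the active arm only. The SAP does not say that this pattern counts as efficacy, but calling the tests a comparison between groups invites that reading.

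**Working it through.** **The SAP's own figure.** Section 2.3 gives 80% power for d = 0.74 with 30 per arm. For a two-sample t-test, noncentrality = 0.74 × √(30/2) = 2.87 on 58 df. The two-sided power is 80.5% and the one-sided power 88.2%, so the stated figure is a two-sided between-arm calculation. The SAP gives no figure for the post-hoc tests.

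**Inputs.** From the SAP: 30 per arm, three visits (baseline, weeks 16 and 24), each effect tested at 0.05. Assumed, because the SAP gives none: within-person correlation 0.5 or 0.7 (compound symmetry), and a drift identical in both arms and equal at weeks 16 and 24, in units of the SD of change. There is no product effect. Each setting has 20,000 simulated trials, with split-plot F tests for time, condition and interaction as the gate.

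**Gate with no drift.** Treating the three tests as roughly independent, 1 − 0.95³ = 14.3%. Simulated: 14.1% to 14.3%.

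**Analytic check of the misleading pattern.** Let π be the power of a one-tailed paired t-test in one arm (n = 30, 29 df, noncentrality = drift × √30). Without a gate, the chance that the active arm is significant and placebo is not is π(1 − π).

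- Drift 0.3: noncentrality 1.64, π = 0.484, product 0.250.
- Drift 0.4: noncentrality 2.19, π = 0.690, product 0.214.
- Drift 0.5: noncentrality 2.74, π = 0.848, product 0.129.
- Drift 0.7: noncentrality 3.83, π = 0.982, product 0.018.

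The gate lowers these values where it is often closed. At 0.5 and 0.7 it is almost always open, and the simulation below agrees with the formula.

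**Simulation of the rule as written** (ranges cover correlation 0.5 and 0.7):

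| Shared drift (SD of change) | Gate open | Active significant, placebo not, week 16 | Same, week 16 or 24 |
|---|---|---|---|
| 0 | 14% | 1.5–1.7% | 2.7–2.8% |
| 0.1 | 20% | 4.5% | 7.1–7.3% |
| 0.2 | 40% | 11% | 17% |
| 0.3 | 69% | 18.3–18.5% | 28.6% |
| 0.4 | 90–91% | 18.9–19.0% | 30% |
| 0.5 | 98.5–98.6% | 12.4–12.8% | 21% |
| 0.7 | 100% | 1.7% | 3.1–3.3% |

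At drifts 0.3 and 0.4, 89% to 91% of the week-16 patterns occur with no significant interaction. A two-sided between-arm test of week-16 change rejects in 4.7% to 5.3% at every drift.

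**If paired is a slip for pairwise.** The tests are then one-tailed between arms under the same gate. A false beneficial result at week 16 or 24 occurs in 3.0% with no drift and in 8.2% to 8.9% at 0.4 SD or more.

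**Proposed rule** (interaction gate, then two-sided between-arm comparisons at the two visits): a false result in either direction occurs in 3.8% to 4.4%. With no gate, the chance that the interaction or either comparison is significant is 9.5% to 10.2%, so a gate is needed.

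**The case against.** - **The ANCOVA already compares the arms.** This stands. The interaction is a valid between-arm test at 0.05 and can answer the objective. The fault lies in the follow-up step, which is labelled a group comparison and does not need that interaction to be significant.
- **Each significant effect may simply receive its matching follow-up.** A paired test between visits is an ordinary follow-up to a time effect and makes no treatment claim. The stated purpose of the sentence is nevertheless to compare groups, and nothing in the SAP confines the paired tests to describing time.
- **The simulated pattern is not a decision rule in the SAP, and the drift is assumed.** Both are true. Under no product effect the reverse pattern (placebo significant, active not) is about as common. The rates illustrate size; the mismatch of test and purpose does not depend on them.
- **Paired may mean pairwise.** Fault 1 is then a wording error, but faults 2 and 3 remain.
- **One-tailed testing is not what inflates the pairwise figure.** This stands. At week 16 alone, the one-tailed between-arm false rate under the present gate is 1.7% to 1.8% with no drift, about 4.5% at 0.4 SD and 5.0% to 5.1% at 0.7 SD. Two-sided tests under the same gate also give 8.5% to 9.1% over both visits at 0.4 SD or more. The excess comes from two visits behind an open gate. The complaint about the tail is that none is named and that the rest of the SAP is two-tailed.
- **These are secondary outcomes of a proof-of-concept trial.** True, and it limits the weight of the point.

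**Conclusion.** The concern holds and should be fixed. As written, the post-hoc rule uses a test that cannot compare the arms, opens it on effects that say nothing about treatment, and leaves the tail open. The first two follow from the wording and the parallel design alone, except that the first becomes a wording error if pairwise was meant.

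The size depends on a shared drift that the SAP does not give. The week-16 pattern is about 2% of null trials with no drift or with 0.7 SD, and peaks near 19% at 0.3 to 0.4 SD; over both visits the peak is about 30%. These rates assume 30 per arm, compound symmetry and correlation 0.5 to 0.7. They measure how often a misleading pattern appears. They are not the type I error of a test the SAP declares.

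The primary HbA1c test and the insulin-sensitivity test are two-tailed and between arms, so the primary conclusion is unaffected.

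**What to change.** Replace the post-hoc sentence in section 5.2.3 with one rule, for example:

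> Baseline, week 16 and week 24 are the levels of time. The treatment effect is judged by the time-by-condition interaction (two-sided, p < 0.05). Only if it is significant are two-sided, unpaired between-arm comparisons of change from baseline to week 16 and to week 24 tested. Estimates with 95% confidence intervals are reported in all cases. A main effect of time opens no efficacy test. Within-arm changes are descriptive only.

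This fits section 5.1.2, which names baseline together with both later visits ("HbA1c (%) between baseline, 16 and 24 weeks"). If baseline is meant as the ANCOVA covariate, it should not also be a level of time. In that case use baseline-adjusted, two-sided arm contrasts at weeks 16 and 24 and name the gate in advance. With the condition effect or the interaction as gate, at least one false contrast occurs in 5.9% of null trials; with the condition effect alone, 4.0%. Apply the same two-sided between-arm comparisons in the trimmed-mean branch.

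The change needs no new data, but within-arm significance and the extra power of a single tail can no longer be claimed. For an effect of 0.74 SD of change at both visits (taking the d of section 2.3 to apply to change), power is:

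- one-tailed between-arm test at week 16 under the present gate: 87% to 88%
- interaction test: 84%
- ungated two-sided comparison at week 16: 80%
- two-sided comparison at week 16 behind the interaction gate: 76%

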5.3 Missing data

Primary and secondary analyses will be performed on the ITT population. Outcome data will be imputed using multiple imputation (11).

5.4 Additional analyses

Exploratory analyses will examine interdependencies of the primary and secondary outcomes, and sub-group analyses including the effects of baseline HbA1c, insulin sensitivity, fasting glucose, sex and age groups on the percent change in HbA1c level.

5.5 Sensitivity analyses

As a sensitivity analysis, the primary and secondary outcomes will be analyzed using the PP population to investigate whether conclusions are sensitive to assumptions regarding the pattern of missing data.

5.6 Statistical software

Python will be used for all statistical analysis.

